8.3.3.3. Complete Data Analysis

If $\geq 10\%$ of participants have missing data in the primary endpoint, a sensitivity analysis using only participants who have at least baseline and Day 42 values will be performed. The MMRM analyses proposed for the analysis of the primary outcome will be provided for change from baseline to Day 42.

8.3.3.4. Supportive Analysis of Primary Endpoint

The primary analysis will be repeated based on the PPS. The WAIS-IV coding score after taking the prohibited medication will not be included in the analysis. No sensitivity analysis will be performed based on the PPS.

8.3.3.5. Subgroup Analyses of Primary Analysis

The primary endpoint will be analyzed for the following subgroups:

- Baseline Modified Hoehn and Yahr Stage: $\leq 2, > 2$

- [REDACTED]
- Age at randomization: ≤ 65 , > 65

Subgroup analyses will only occur if there are at least 10 participants for each subgroup.

By-participant listing by visit will be provided.

— 1 —

© 2013 Pearson Education, Inc.

© 2013 Pearson Education, Inc.

10 of 10

Digitized by [contact]

Digitized by [contact]

Digitized by [contact]

© 2013 Pearson Education, Inc.

11. *Leucosia* (Leucosia) *leucosia* (Linnaeus, 1758) (Fig. 11)

© 2013 Pearson Education, Inc.

For more information, contact the Office of the Vice President for Research and Economic Development at [contact] or [contact].

Digitized by [contact]

© 2013 Pearson Education, Inc.

© 2019 Pearson Education, Inc. All Rights Reserved. May not be copied, scanned, or duplicated, in whole or in part. Due to electronic rights, some third party content may be suppressed from the eBook and/or eChapter(s). Editorial review has determined that any suppressed content does not materially affect the overall learning experience. Pearson Education, Inc. reserves the right to remove additional content at any time if subsequent rights restrictions require it.

11. **What is the primary purpose of the *Journal of Clinical Endocrinology and Metabolism*?**

For more information, contact the Office of the Vice President for Research and Economic Development at [contact] or [contact].

For more information, contact the Office of the Vice President for Research and Economic Development at [contact] or [contact].

© 2013 Pearson Education, Inc.

For more information, contact the Office of the Vice President for Research and Economic Development at [contact] or [contact].

[REDACTED]

8.3.4.6. Penn Parkinson's Daily Activities Questionnaire-15 Knowledgeable Informant

For each PDAQ-15 KI item and total score, a summary using descriptive statistics on observed values and changes from baseline will be provided.

The change from baseline to Day 42 and Day 70 on the PDAQ-15 KI total score will be analyzed using a similar MMRM model described in [Section 8.3.3.1](#). A plot showing the LSM \pm SE bar over time within each treatment group will also be provided.

By-participant listing by visit will be provided.

A large grid of black horizontal bars on a white background. The bars are of varying lengths, creating a pattern of horizontal lines of different widths. The grid is composed of approximately 20 rows and 10 columns of bars.

A large grid of black horizontal bars on a white background, representing a redacted document. The bars are of varying lengths and are arranged in a grid pattern. There are approximately 15 rows of bars, with each row containing between 1 and 5 bars. The bars are solid black and have a consistent thickness. The grid is centered on the page and covers most of the available space.

8.3.4.14. Daily (Mobile Phone-Based) Assessments

For PVT and DSST, invalid data will be flagged after science team review by the vendor and will not be used for the analysis.

For key outcome measures specified in [Section 8.3.1.2.13](#), the change from baseline to Day 14 and Day 42 will be summarized using descriptive statistics and analyzed using a similar MMRM model described in [Section 8.3.3.1](#). A plot showing the LSM \pm SE bar over time within each treatment group will also be provided.

Other outcome measures specified in [Section 8.3.1.2.13](#) will be summarized by visit using descriptive statistics.

By-participant listing by visit will be provided.

8.4. Safety Analysis

All safety summaries will be performed on the Safety Set using treatment received.

Safety and tolerability of SAGE-718 oral capsule in participants with PD-MCI is the secondary objective of this study and will be evaluated by the frequency and severity of TEAEs and withdrawal due to AEs. Other safety endpoints include change from baseline in vital signs, clinical laboratory analytes, ECGs, and [REDACTED].

The safety endpoints evaluated at scheduled visits are taken as done in nominal visit, without any windowing. If a value is available for a nominal scheduled visit, that value will be used in summary by visit. Unless specified, unscheduled measurement and ET measurement will be included only if a scheduled measurement is not available, and the unscheduled measurement and ET measurement falls within the visit window for the scheduled visit (same as WAIS-IV Coding Test in [Table 3](#)). If there are two or more measurements in a visit window, the measurement taken closest to the study day target will be used in analysis. If the two have same distance from the target study day, the latter one will be used.

Anytime on treatment, last value on treatment and last value on study will be included in the summaries, unless specified. Anytime on treatment is defined as measurement on or after first dose, on or before the date of last dose. Last value on treatment is defined as the last post-baseline value between first dose of IP and up to the date of last dose of IP (inclusive). Last value on study is defined as the last post-baseline value on or after the first dose of IP and on or before the last date of the study.

No statistical hypothesis testing will be conducted.

Safety data will be listed by treatment group and participant and summarized by treatment group.

Table 8. Summary of Safety Analysis

Safety Evaluation	Incidence	Source Data	Change from Baseline	Shift from Baseline	Potentially Clinically Significant	Abnormality/ Clinical Significance
AEs	X					
Clinical Laboratory		X	X	X	X	*
ECG		X	X		X	*
Vital Signs		X	X		X	
Physical Exam		*				

ECG = Electrocardiograms; [REDACTED]
X = Safety Assessment will be summarized in tables
* = Safety Assessment will be listed in individual participant data listings

8.4.1. Adverse Events

AEs will be coded using MedDRA version 22.0 or higher. Intensity/severity and relationship of AE will be evaluated by the investigator.

A TEAE is defined as any AE on or after the first dose of IP or any worsening of a pre-existing medical condition/AE with onset after the start of IP and throughout the study. The analysis of AEs will be based on the concept of TEAEs. Where the AE start date is missing, adverse events will be assumed to be treatment-emergent, unless there is clear evidence (through comparison of partial dates) to suggest that the adverse event started prior to the first dose of study treatment. Missing or partial dates will be imputed for AE. The algorithm for missing or partial start /end date is documented in [Appendix C](#).

Adverse events are assigned an AE period based on the onset date/time. AE periods are defined as follows:

- Pre-treatment AE: AE onset date/time before first IP dosing date/time
- TEAE: AE onset date/time on or after the first IP dose date/time (If an AE start date same as IP first dose date, but no time either in AE start or treatment start, then consider this AE to be in treatment period TEAE.)

- On-treatment TEAE: AE onset date/time on or after first IP dose date/time and on or before IP last dose date + 30 days (Note that time does not matter for the end of this period. i.e., if AE occurred after the last dose but on the same date of last dose, it is considered as on-treatment TEAE)
- Post-treatment TEAE: AE onset date on or after IP last dose date + 31 days

An overall summary of TEAEs will include the number and percentage of participants in the following categories:

- Any TEAE (On-treatment, Post-treatment)
- TEAEs by maximum severity (severe > moderate > mild)
- Any related TEAEs
- Any related TEAEs by maximum severity
- Any serious TEAEs
- Any serious related TEAEs
- Any TEAEs leading to death
- Any TEAEs leading to IP withdrawal
- Any TEAEs leading to withdrawal from the study
- Any TEAEs leading to IP interruption.

Incidence of TEAEs in following categories will be provided by SOC and PT. A participant is counted only once under each SOC and PT in case of multiple occurrences of the same AE. These tables will be sorted by decreasing frequency of SOC in SAGE-718 group, then in placebo group, then alphabetically first within SOC, then within PT.

- TEAEs
- On-treatment TEAEs
- Post-treatment TEAEs
- TEAEs by maximum severity
- TEAEs by causality (related, not related) to IP
- TEAE by maximum severity and causality to IP
- Serious TEAEs
- TEAEs leading to IP withdrawal
- TEAEs leading to withdrawal from the study
- TEAEs leading to IP interruption.

Additionally, incidence of TEAEs will be summarized by PT. Most frequent TEAEs reported >5% in PT of the combined treatment group will also be summarized by PT.

For maximum severity, participants will be counted only once within each SOC and PT at the maximum severity in the following order: severe > moderate > mild; an AE with missing severity will be omitted from severity presentation and will not be imputed. For relationship to IP, participant will be counted only once within each SOC and PT with the strongest relationship to IP in the following order: related > not related; an AE with relationship missing is treated as related. For seriousness, an AE with missing seriousness will not be imputed. The incidences will be presented by descending frequency of SOC and then, within a SOC, by descending frequency of PT based on the participant count, and in alphabetical order of PT if the incidence within a PT is a tie.

In addition, TEAE summaries by SOC/PT will also be presented by the following subgroups:

- Race (Black or African American, White, Other)
- Sex (Male, Female)
- BMI (≤ 18.4 , $18.5\text{-}24.9$, $25\text{-}29.9$, $\geq 30 \text{ kg/m}^2$; Categories are defined after rounding)
- Age at randomization: ≤ 65 , > 65 years

A by-participant listing of all AEs, SAEs (including those with onset or worsening before the start of IP), TEAEs leading to death, TEAEs leading to IP withdrawal through the end of the study, and most frequent (5%) TEAEs will be provided.

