4.2. Safety Endpoints

- To evaluate the safety and tolerability of SAGE-718 in participants with PD-MCI
 - Proportion of participants experiencing treatment-emergent adverse events (TEAEs) and severity of TEAEs.
 - Number of participants who withdraw due to adverse events (AEs).
- To evaluate the safety and tolerability of SAGE-718 on other safety parameters.
 - Change from Baseline in vital signs, clinical laboratory parameters, electrocardiograms (ECGs), and [REDACTED]
[REDACTED]
 - [REDACTED]
 - [REDACTED]

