8. STATISTICAL ANALYSIS

8.1. General Considerations

Continuous data will be summarized in terms of the number of participants, mean, standard deviation (SD), minimum value (min), maximum value (max), median, 25th percentile (Q1), and 75th percentile (Q3). The minimum and maximum will be reported with the same number of decimal places as the source (raw) data. Mean, median, Q1, and Q3 will be reported to 1 decimal place more than the source (raw) data. SD and standard error (SE), if applicable, will be reported to 2 decimal places more than the source (raw) data. Least Square Means (LSM) will be reported to 1 decimal place more than the source (raw) data. Confidence intervals (CI) will be presented to one more decimal place than the associated parameter estimate. In general, the maximum number of decimal places reported shall be four for any summary statistic.

Any values that require transformation to standard units (metric or SI) will be converted with the appropriate corresponding precision.

Categorical data will be summarized in terms of the number of participants providing data at the relevant time point (n), frequency counts, and percentages. Percentages will be presented to 1 decimal place unless otherwise specified. Any planned collapsing of categories will be detailed in the SAP text and the data displays.

Percentages will not be presented for zero counts. Percentages will be calculated using the number of participants (n) as the denominator. A missing category shall be included only for categorical variables where no data is available. The missing category will be omitted if there are no missing values for that variable.

All participant data, including those that are derived, that support the tables and figures will be presented in the participant data listings. Some data may be presented only in participant data listing, some may be presented with a corresponding table or figure; these will be indicated in relevant sections below. All summaries will be provided by treatment – either by randomized treatment or actual treatment received.

If a participant takes any dose of SAGE-718, the participant's actual treatment is considered as SAGE-718, regardless of the treatment to which the participant has been randomized.

P-values will be reported to four decimal places, with p-values less than 0.0001 reported as "<0.0001". P-values larger than 0.9999 will be reported as ">0.9999".

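### TEAEs with no severity grade are left out of every severity table, so counts of severe or at least moderate TEAEs can be too low, and the tables will not show how many are ungraded

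*SAP*

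**What the plan says.** SAP 4.2 lists as its first safety endpoint "Proportion of participants experiencing treatment-emergent adverse events (TEAEs) and severity of TEAEs". Protocol Section 5 places the same endpoint under the secondary objectives.

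SAP 8.4.1 sets the counting rule for severity: "participants will be counted only once within each SOC and PT at the maximum severity in the following order: severe > moderate > mild". It then adds that "an AE with missing severity will be omitted from severity presentation and will not be imputed".

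The same section handles other missing AE fields as follows:

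- Relationship: "an AE with relationship missing is treated as related".
- Seriousness: "For seriousness, an AE with missing seriousness will not be imputed".
- Start date: "Where the AE start date is missing, adverse events will be assumed to be treatment-emergent", unless partial dates clearly show an earlier onset.

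The severity rule reaches several displays. In the overall summary it affects all TEAEs and related TEAEs by maximum severity. By SOC and PT it affects the table by maximum severity and the one described as "TEAE by maximum severity and causality to IP". In Appendix E the overall summary is Table 14.3.1.1, and the severity-by-causality table is Table 14.3.1.3.

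On categorical summaries in general, SAP 8.1 says: "The missing category will be omitted if there are no missing values for that variable". It bases percentages on n, the participants who provide data. SAP 8.4.1 does not say which denominator the severity tables use.

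**The concern.** Leaving out an ungraded event looks neutral, but in a maximum-severity table it is not. The participant is classified by whatever graded events remain, so the ungraded event is in effect assumed to be no worse than those. If there are no graded events, the participant drops out of the severity rows while still counting under any TEAE. The severity rows then fail to add up to the any-TEAE row, and no footnote is planned to explain the gap. The same happens for related TEAEs: a participant whose only related TEAE is ungraded counts as having a related TEAE but has no entry in the related-by-severity rows.

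At stake is the descriptive account of how severe the TEAEs were. In a trial of this size a single participant visibly changes a severe-TEAE percentage.

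**Working it through.** The plan states no figure to reproduce, so the check is of the counting rule itself.

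**Step 1. One participant.** Take a participant whose graded TEAEs have a given maximum, and add one ungraded TEAE whose true grade is mild, moderate or severe. The table shows the maximum severity under omission against the true maximum, which is the higher of the recorded maximum and the true grade of the ungraded event.

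| Recorded maximum | Shown under omission | Truth if ungraded event is mild | ... moderate | ... severe |
|---|---|---|---|---|
| none | no row | mild | moderate | severe |
| mild | mild | mild | moderate | severe |
| moderate | moderate | moderate | moderate | severe |
| severe | severe | severe | severe | severe |

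In 6 of the 12 combinations the displayed grade is below the truth, in 6 it is equal, and in none is it above. These are cases, not probabilities. It follows that the counts of participants with a severe TEAE, and with an at least moderate TEAE, can only be equal to the truth or too low.

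**Step 2. One arm.** Inputs: about 76 participants randomized 1:1 (SAP 5.2), so 76/2 = 38 per arm, taken here as the Safety Set denominator. The true maximum severities are an assumption for illustration: 12 mild, 6 moderate, 2 severe, so 20 participants with any TEAE. The true severe rate is 2/38 = 5.3%.

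- *One severe TEAE is ungraded and is that participant's only TEAE.* Severe becomes 1/38 = 2.6%. The severity rows add to 12 + 6 + 1 = 19, against 20 with any TEAE.
- *One severe TEAE is ungraded and that participant also has a graded mild TEAE.* Severe becomes 1/38 = 2.6%, and mild rises from 12/38 = 31.6% to 13/38 = 34.2%. The rows still add to 13 + 6 + 1 = 20, so nothing looks amiss.
- *Three participants whose only TEAE was mild have no grade.* Severe stays at 2/38 = 5.3%. If the denominator were participants with a graded TEAE, the severe share would rise from 2/20 = 10.0% to 2/17 = 11.8%.

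**Step 3. Between arms.** Suppose each arm truly has 2/38 severe. One ungraded severe case moves the SAGE-718 minus placebo difference to (1 - 2)/38 = -2.6 points if it is in the SAGE-718 arm, and to (2 - 1)/38 = +2.6 points if it is in the placebo arm.

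**Step 4. What the alternatives show.** In the three-mild example, a Missing row gives 9 + 6 + 2 + 3 = 20, which reconciles with any TEAE. Counting the three as severe gives 5/38 = 13.2% against a true 5.3%, which is too high. The two displays together bracket the truth: at least 2/38, at most 5/38. In general the bracket is up to 1/38 = 2.6 points wide for one affected participant, 2/38 = 5.3 for two and 3/38 = 7.9 for three.

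The second example in Step 2 shows why a Missing row alone is not enough: that participant already sits in the mild row. Only a count of participants with any ungraded TEAE makes the case visible.

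**The case against.** The case for leaving the rule alone has several parts.

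- **Not imputing is the plan's general position.** Protocol 12.2 rules out imputation of missing data, and SAP 8.1 repeats this unless otherwise specified. Missing seriousness is not imputed either. This stands as an argument against entering a grade in the main table, but not against showing that a grade is missing.
- **There is no outright contradiction.** A reader might infer that the severity rule conflicts with the rule for missing relationship and with SAP 8.1. The documents do not go that far. Relationship has two levels and severity three, and SAP 8.4.1 may set a specific rule that departs from a general default. The sentence in SAP 8.1 just before the one quoted is also restrictive and not clear. What remains is that SAP 8.1 envisages a missing category in some form, and that SAP 8.4.1 gives no reason for doing without one here.
- **The consequences are limited.** Ungraded TEAEs are left out of the severity displays only. They stay in the any-TEAE, SOC/PT and causality tables and in the by-participant listing, and no hypothesis test is done on safety data. Protocol 11.2.5 requires intensity for each AE, and Protocol 13.1 has monitors confirm that AEs are properly documented. All of this stands, and it is why the expected effect is small.
- **Counting every missing grade as severe would distort the main table.** This also stands, as the 13.2% against 5.3% shows. It is a reason to confine that count to a sensitivity display.

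**Conclusion.** The point holds in a limited form. If any TEAE lacks a grade, SAP 8.4.1 can understate the number of participants with severe or at least moderate TEAEs, and the tables will not show how many are affected. If no grade is missing, nothing changes.

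A reader might infer that the severity endpoint as a whole can only be understated. That does not follow: the mild and moderate cells, the shares among graded participants and the difference between arms can each move either way. The one-sided direction belongs to the counts of severe and at least moderate TEAEs. It carries over to their percentages only when the denominator is fixed.

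The size is 2.6 percentage points per affected participant, assuming 38 per arm. How many would be affected cannot be worked out from the documents, which give no rate of missing grades. The number is probably small. The change is worth making because it is nearly free and removes an ambiguity that a reader of the tables could not otherwise detect.

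**What to change.** In SAP 8.4.1, replace the omission rule with wording to this effect: *TEAEs with missing severity are not imputed in the main severity tables but are kept in a Missing row (Table 14.3.1.1, Table 14.3.1.3 and the other maximum-severity displays). The Safety Set is the denominator. A footnote gives the number of participants per arm who have any ungraded TEAE, including those shown at a lower recorded grade. If any grade is missing, a sensitivity display counts those TEAEs as severe.*

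The main tables then respect the no-imputation position in Protocol 12.2. The sensitivity display is an exception stated in advance, which SAP 8.1 allows for.

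The cost is one amended rule, one row or footnote per table and, only if a grade is missing, one further display whose severe count may look slightly less favourable. It should be settled before database lock, when the SAP is due to be final.

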8.4.2. Clinical Laboratory

Any lab results considered clinically significant by the investigator will be captured as adverse events, hence will show up in AE displays.

For the laboratory results that are " $\leq x$ " or " $\geq x$ ", where x is a number as collected in the data, the numeric part of the result will be used in the calculation in the summary tables. If a laboratory value is reported as " $< y$ " then y minus the minimum value with the same precision as y (e.g., if y = 1.345, then use y - 0.001) will be used for the analysis. If a laboratory value is reported as " $> y$ " then y plus the minimum value with the same precision as y will be used for the analysis. The same is true if the result is presented as below limit of quantification (BLQ) and a lower limit of quantification (LLOQ) value is provided; the LLOQ value will be used for calculation in the summary tables. The actual results as collected will be displayed in the listings.

Results of continuous clinical laboratory parameters for hematology, biochemistry, coagulation, and urine samples for urinalysis at each scheduled visit and mean changes from baseline will be summarized in standard units. In addition, it will also include the summary of the last value on treatment and the last value on study.

Normal ranges for each parameter will be provided by the laboratory. Shift from baseline to post-baseline values in abnormality of hematology and biochemistry results will be

summarized. In addition, shift from baseline to worst post-baseline values in abnormality of results at any time on treatment, the last value on treatment (on or after first dose, on or before last dose) and the last value on study (after last dose, on or before last day of the study) will be summarized. If a participant has both low and high post-baseline records, the participant will be counted twice for each low and high cell.

Clinical laboratory results will be listed by participant and timing of collection for each treatment group.

The number and percentage of participants with potentially clinical significance (PCS) values for each laboratory parameter will be summarized by treatment for anytime on treatment, the last value on treatment and the last value on study. Sponsor determined PCS values will be identified for specific laboratory parameters as outlined in [Table 9](#) below.

Table 9. Potentially Clinically Significant Values for Specific Laboratory Parameters

Laboratory Parameter	Sex	Units	Criteria for PCS Values (Observed values)	
			High	Low
Hematology				
Hemoglobin	Male	g/L	>185	<115
	Female	g/L	>170	<100
Hematocrit	Male	Fraction of 1	>0.55	<0.385
	Female	Fraction of 1	>0.49	<0.345
Platelet count		10 ⁹ /L	>600	<125
White blood cell		10 ⁹ /L	>15	<2.5
Basophils		10 ⁹ /L	>0.5	NA
Eosinophils		10 ⁹ /L	>1.5	NA
Neutrophils		10 ⁹ /L	NA	<1.5
Lymphocytes		10 ⁹ /L	>6.0	<0.5
Monocytes		10 ⁹ /L	>1.4	NA
Serum Chemistry				
Albumin		g/L	>70	<28
Blood urea nitrogen		mmol/L	>10.71	NA
Calcium		mmol/L	>2.75	<2.0
Chloride		mmol/L	>120	<90

Laboratory Parameter	Sex	Units	Criteria for PCS Values (Observed values)	
			High	Low
Creatinine		mmol/L	>3xULN or >3x Baseline	
Gamma Glutamyl Transferase			>3xULN	
Glucose		mmol/L	>13.9	<2.8
Sodium		mmol/L	>150	<132
Potassium		mmol/L	>5.4	<3.3
Protein		g/L		<45
Bicarbonate		mmol/L	>34	<18
Phosphorus		mmol/L	>1.94	<0.61
Coagulation				
Prothrombin time			≥1.11xULN	NA
Partial thromboplastin time			>1.5 xULN	NA

Liver function tests will be monitored closely for PCS values, and will be summarized for occurrence any time post-baseline for the following parameters for these PCS threshold:

- Alanine Aminotransferase: >3xULN, >5xULN, >10xULN
- Aspartate Aminotransferase: >3xULN, >5xULN, >10xULN
- Alanine Aminotransferase or Aspartate Aminotransferase: >3xULN, >5xULN, >10xULN
- Alkaline Phosphatase: >1.5xULN, >2xULN
- Total Bilirubin: >1.5xULN, >2xULN
- Total Bilirubin >2xULN **AND** (Alanine Aminotransferase or Aspartate Aminotransferase >3xULN) [any time post-baseline, does not need to be measured at the same time point of assessment]
- [(Total Bilirubin >2xULN) **AND** Alkaline Phosphatase <2xULN (any time post-baseline, measured at the same time point of assessment)] **AND** [(ALT or AST >3xULN) **AND** Alkaline Phosphatase <2xULN (any time post-baseline, measured at the same time point of assessment)]

Note: The conditions in the first pair of brackets do not need to occur at the same timepoint as the conditions in the second pair of brackets.

By-participant listing of FSH and serology test results at screening will be provided.

By-participant listing of urine drug screen and breath alcohol test will also be provided.

8.4.3. 12-Lead Electrocardiogram

A single 12-lead ECG under Protocol Amendment 2 and triplicate 12-lead ECG under Original Protocol and Protocol Amendment 1 will be performed after the participant has been resting in the supine position for at least 5 minutes. If the multiple 12-lead ECG are performed, the average of all values on the same date will be used in the summary. If there are both scheduled visit and unscheduled visit on the same date, all the assessments on that date are considered as the scheduled visit for the summary. A summary of the observed values (raw values for the single ECG; average values for the multiple ECG on the same date) and change from baseline values will be summarized by each scheduled visit for the following ECG parameters: heart rate, PR, QRS, QT, and QTcF interval. This summary will also include the last values on treatment and on study. A by-participant listing of 12 lead ECG will also be provided for each of the ECG measurements.

ECG is evaluated by investigator as "normal", "abnormal, not clinically significant" and "abnormal, clinically significant". The number and percentage of participants with each category will be provided at baseline and each post-baseline scheduled assessment time point. If there are more than one evaluation at the same time point, the latest assessment from ECG vendor will be used for the summary.

Potentially clinically significant values of QTcF as outlined in [Table 10](#) will be summarized by treatment for anytime on treatment, the last value on treatment and the last value on study.

Table 10. Potentially Clinically Significant (PCS) Values for 12-Lead ECG Parameter

12-Lead ECG	Units	Criteria for PCS Values (Observed values)		Criteria for PCSC values (Change from Baseline)	
		High	Low	Increase	Decrease
QTcF	msec	>450 but \leq 480 >480 but \leq 500 >500	NA	\geq 30 to 60 >60	NA

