^m Clinical laboratory assessments will include blood samples for hematology, biochemistry, coagulation, and urine samples for urinalysis. Samples will be collected prior to dosing on days when IP is administered. On nondosing days, collection may occur at any time.

ⁿ Serum pregnancy tests will be conducted for all female participants at Screening; urine pregnancy tests will be conducted at other scheduled time points for female participants who are not postmenopausal or surgically sterile.

^o Refer to [Table 3](#) for details.

[REDACTED]

[REDACTED]

[REDACTED]

[REDACTED]

^r PDAQ-15 Knowledgeable Informant is provided by caregiver.

[REDACTED]

^t Daily reminders will be sent to participants via a mobile device to complete assessments on remote device. Daily assessments include the [REDACTED] DSST, PVT, and the National Sleep Foundation Sleep Diary. It is recommended that assessments are completed at approximately the same time each day, within 1 hour following IP administration. Daily mobile assessments should be completed in a quiet area of participant's home. On dosing days the remote assessment will be completed in the clinic following dosing under observation by the study staff.

^u On Days 1, 14, and 42, the participants will self-administer IP in the clinic under the supervision of study staff. All scheduled safety assessments will be conducted prior to dosing and all scheduled cognitive tests will be administered postdosing.

^v Study staff will dispense enough IP for the participant to take daily at home until the next scheduled visit.

^w Participants will bring all used packaging and unused IP to the clinic at each visit for study staff to review and document.

^x AEs/SAEs collected from time of ICF throughout the duration of participation.

^y At Screening, to include all medications and supplements taken within 60 days and all medications used to treat PD regardless of timing. At subsequent visits, all changes to any medication should be captured.

Table 3: Schedule of [REDACTED], Biochemical, and Genetic Sampling

Assessments	Screening	Baseline	Treatment		Follow-Up	
	Days -28 to -8	Day -7 (± 2 days)	Day 1	Day 14 (± 2 days)	Day 42 (-2 days)	Day 70 (± 4 days) or ET
[REDACTED]						
Predose				X	X	X
Optional blood collection: biochemical research ^b						
	X			X	X	
Optional blood collection: genetic research						
	X					

Abbreviations: ET = early termination; IP = investigational product; [REDACTED]

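### SAP 8.4.3 averages all ECGs taken on one date, scheduled and unscheduled, and on the natural reading that average feeds the Table 10 QTcF outlier categories.

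*SAP*

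**What the plan says.** SAP 8.4.3 (12-Lead Electrocardiogram) sets two handling rules. For repeated tracings: "If the multiple 12-lead ECG are performed, the average of all values on the same date will be used in the summary". For scheduled and unscheduled visits that coincide: "If there are both scheduled visit and unscheduled visit on the same date, all the assessments on that date are considered as the scheduled visit". The by-visit output is then described as "A summary of the observed values (raw values for the single ECG; average values for the multiple ECG on the same date".

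The outlier analysis has its own paragraph. It takes its QTcF limits from Table 10 and says that the flagged readings "will be summarized by treatment for anytime on treatment, the last value on treatment and the last value on study". The Table 10 column for absolute values is headed "Criteria for PCS Values (Observed values". Its bands are >450 to 480, >480 to 500 and >500 ms, with increases from baseline of 30 to 60 and >60 ms.

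The same section records one ECG per time point under Protocol Amendment 2 and three under the original protocol and Amendment 1. It also promises a by-participant listing of each ECG.

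**The concern.** Averaging a planned triplicate taken together is ordinary practice. This rule is wider. It pools every ECG that shares a calendar date, whatever its purpose or time, including one taken for symptoms or to check an abnormal trace.

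For by-visit means this matters little. For an outlier table it works against the purpose, because the bands exist to show individual extremes and the average pulls an extreme towards the ordinary readings. The by-arm count of participants above 500 ms, or with an increase above 60 ms, could then be too low. The same event would also be classified differently according to how many ECGs the protocol version in force required. Safety and tolerability is the study's secondary objective, and ECG change is among its listed endpoints.

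**Working it through.** The plan gives no figure to reproduce, so the check has two parts: whether the average reaches Table 10, and what it does there.

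**Does the average reach Table 10?**

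- SAP 8.4.3 glosses ECG observed values as the raw value for a single ECG and the same-date average for several. Table 10, in the same section, applies its cut-offs to observed values.
- No sentence says that Table 10 uses individual or highest readings. None says outright that it uses averages.
- SAP 8.4 defines the anytime-on-treatment period by measurement, without saying whether that means an individual or an averaged value.
- Elsewhere the SAP keeps extremes intact. SAP 8.4.2 tabulates shifts to the worst post-baseline laboratory value and counts liver test thresholds at any time after baseline.

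A programmer following 8.4.3 would most naturally use the average.

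**What does the average do?**

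Inputs from the SAP: the Table 10 bands, and k = 1 (single) or k = 3 (triplicate) scheduled ECGs. Assumed inputs, because the documents give no QTcF data: baseline 425 ms, scheduled mean s = 430 ms, one unscheduled reading u = 505 ms on the same date.

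Average = (u + k·s)/(k + 1).

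| Basis | QTcF (ms) | Change (ms) | Bands met |
|---|---|---|---|
| Unscheduled reading alone | 505 | 505 − 425 = +80 | >500; >60 |
| k = 1 | (505 + 430)/2 = 467.5 | +42.5 | >450–480; 30–60 |
| k = 3 | (505 + 3×430)/4 = 448.75 | +23.75 | none |

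**How sensitive is this to the assumed values?** The average is at or below a cut-off T when s ≤ (T(k + 1) − u)/k.

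| u (ms) | Leaves >500, k = 1 | Leaves >500, k = 3 | Leaves all absolute bands, k = 1 | Leaves all absolute bands, k = 3 |
|---|---|---|---|---|
| 501 | s ≤ 499 | s ≤ 499.7 | s ≤ 399 | s ≤ 433.0 |
| 505 | s ≤ 495 | s ≤ 498.3 | s ≤ 395 | s ≤ 431.7 |
| 510 | s ≤ 490 | s ≤ 496.7 | s ≤ 390 | s ≤ 430.0 |
| 520 | s ≤ 480 | s ≤ 493.3 | s ≤ 380 | s ≤ 426.7 |

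Losing the >500 band is therefore the usual result under either scheme. Losing every absolute band under the single-ECG scheme needs a low scheduled value: 395 ms or less for a 505 ms reading, a gap of 110 ms. Under triplicates it happens at ordinary values, but narrowly. With s = 432 the average is (505 + 1296)/4 = 450.25 ms and is flagged. With s = 430 and a baseline of 418, the change is 448.75 − 418 = +30.75 ms and is flagged.

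**The case against.** The strongest reply is that the averaging sentences belong to the paragraph on by-visit summaries, while the outlier values have a separate paragraph with different periods. Protocol 12.6.5 makes the same division between mean ECG data by visit and potentially significant QTcF by treatment. Observed values is also a generic heading, used in Tables 9 and 11. This stands in part: the link to Table 10 is the natural reading and not an outright statement. It does not remove the point, because 8.4.3 itself tells the reader what observed values means for ECGs, and the most favourable reading still leaves the input to Table 10 unstated.

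Two stronger readings are tempting. A reader might infer that the plan makes QTcF values above 500 ms vanish from the tables. The documents do not support that as a general result. Under the current single-ECG scheme the usual effect is a lower band, and disappearance at ordinary values needs the superseded triplicate scheme. A reader might also infer that pre-dose and post-dose ECGs are being mixed, because on in-clinic dosing days "All scheduled safety assessments will be conducted prior to dosing". That is possible, but nothing says when an unscheduled ECG is taken. An immediate repeat could also be pre-dose, and there is no dosing at Day 70.

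The opportunity is limited too. Table 2 schedules post-baseline ECGs only on Days 14, 42 and 70 (or early termination), and an unscheduled ECG on any other date is not pooled with a scheduled one. Every ECG is listed. Under Protocol 11.2.1, ECG changes that the investigator judges clinically significant, or that lead to treatment or to interruption or discontinuation of study treatment, are adverse events and so enter the by-arm adverse event tables. These safeguards limit the harm. They do not correct the by-arm QTcF count, and Listing 16.2.9.1.2 would miss the reading too if it were built on averages.

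**Conclusion.** The point holds, with minor to moderate weight. As written, and on the natural reading, SAP 8.4.3 dilutes an extreme QTcF that shares a date with ordinary readings before the Table 10 bands are applied. In the illustration, the participant drops from >500 to >450–480 ms and from >60 to 30–60 ms under the current scheme, and meets no band under the earlier one.

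This rests on Table 10 using the section's own meaning of observed values and on assumed QTcF values. The documents show neither how often same-date ECGs occur nor how many participants had triplicates. They therefore support a claim about the rule, not a claim that any participant's reading has been missed.

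**What to change.** - Keep averaging for the by-visit descriptive statistics, but only within planned replicates at one time point.
- State that Table 10 and Listing 16.2.9.1.2 never average unscheduled ECGs with scheduled ones.
- For the anytime-on-treatment rows, use the highest QTcF in that period, with a planned triplicate counting as its mean and each unscheduled ECG entered separately.
- For the two last-value rows, use the last such time point in the period concerned.

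The cost is a few sentences and one extra derivation, with no new data and no change in conduct. Slightly more flags may appear, and participants with more ECGs have somewhat more chance of one. A single ECG would still enter as a raw value and a triplicate as a mean, so some dependence on protocol version remains and deserves a table footnote.
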